5.1 Efficacy assessments

5.1.1 DAS 28

The DAS28 is a composite, validated index for measuring disease activity in RA and is calculated at timepoints indicated in [Table 1](#). The DAS28 (CRP) has been validated against radiographic progression and physical function (HAQ-DI), and the validation profile is similar to the DAS28 (ESR; [Wells et al, 2009](#)).

The DAS28 (CRP/ESR) considers 28 of the 68 TJC and 28 of the 66 SJC and subject's global health (GH) using PGA of disease activity using the VAS of 0 (= best), 100 (= worst) plus levels of CRP (mg/L) or ESR (mm/Hour).

DAS28(CRP) values will be calculated as follows ([Wells et al, 2009](#)):

$$\text{DAS28(CRP)} = 0.56 \times \text{square root (sqrt)} (\text{TJC28}) + 0.28 \times \text{sqrt}(\text{SJC28}) + 0.014 \times \text{GH} + 0.36 \times \ln(\text{CRP}+1) + 0.96$$

DAS28(CRP) values will be calculated at screening for eligibility assessment using an online calculator (ref link <http://www.4s-dawn.com/DAS28/>)

DAS28(CRP/ESR) IDAS 28 (CRP/ESR) Improvement			
Background DAS28(CRP/ESR) Score at Time of DAS28 Improvement Assessment	Level of Improvement from Baseline		
	> 1.2	≥ 0.6 to ≤ 1.2	< 0.6
< 3.2	Good response	Moderate response	No response
≥ 3.2 to ≤ 5.1	Moderate response	Moderate response	No response
> 5.1	Moderate response	No response	No response

DAS28(CRP/ESR) = Disease Activity Score in 28 joints using C-reactive protein/erythrocyte sedimentation rate. Note: DAS28(CRP/ESR)-defined remission is DAS28 (CRP/ESR) of < 2.6. Low disease activity is < 3.2 and high disease activity is > 5.1.

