3.5.2 Other exploratory outcomes

DAS28 will be used for additional comparison between AZD9567 and Prednisolone 20mg, by means of:

- European League Against Rheumatism (EULAR) response criteria.
- DAS28 remission.

- Clinically important change in DAS28 score.
- Low disease activity based on DAS28 score.

Improvement (can be either positive or negative and is defined as post-baseline minus baseline) in DAS28 score will be calculated at each post-baseline scheduled assessment and categorised using the EULAR response criteria in [Table 1](#). Good, moderate or no response will be determined by the DAS28 score at Day 8, 15 and 28 against the level of improvement (mean change from baseline in DAS28 at Day 8, 15 and 28).

Table 1 DAS28 EULAR Response

DAS28 improvement			
Background DAS28(CRP) Score at Time of DAS28 Improvement Assessment	Level of Improvement from Baseline		
	> 1.2	≥ 0.6 to ≤ 1.2	< 0.6
< 3.2	Good response	Moderate response	No response
≥ 3.2 to ≤ 5.1	Moderate response	Moderate response	No response
> 5.1	Moderate response	No response	No response

DAS28: Disease Activity Score in 28 joints. DAS28(CRP): Disease Activity Score in 28 joints using C-reactive protein/erythrocyte sedimentation rate.

DAS28 remission:

- DAS28 score < 2.6

Clinically important change:

- Improvement from baseline in DAS28 score > 1.2

Low disease activity:

- DAS28 score ≤ 3.2

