4.1.4 Table outputs

In general, all summaries will be split by treatment and occasionally added total as follows:

Number (%) of subjects		
AZD9567	Prednisolone	Total

Continuous data will be summarised by descriptive statistics including number of subjects (n), mean, standard deviation (SD), median and range (i.e. minimum value and maximum value). Additionally, the first and third quartiles will be presented for continuous data summaries of exposure data, laboratory parameters and vital signs parameters. For log transformed data, the following descriptive statistics will be presented: number of subjects (n), geometric mean, geometric SD, median and range (i.e. minimum value and maximum value). The mean and median will be presented with one more decimal place than the original data. Standard deviation with two more decimal places than the original data. Minimum and maximum values with the same number of decimal places than the original data.

For categorical data, the variable counts and percentage n (%) per treatment group will be presented. Summaries of continuous variables will be based on non-missing observations. Unless otherwise stated, percentages will be calculated relative to total number of subjects in the analysis set and treatment group. Percentages will be rounded to 1 decimal place.

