4.3.3.5 Other exploratory outcomes

EULAR responses, DAS28 remission, clinically important change in DAS28 and low disease activity based on DAS28 score will be summarised separately by treatment group and visit to Day 28 using counts and percentages. No formal statistical testing will be done.

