6. CHANGES OF ANALYSIS FROM PROTOCOL

Table 2 Summary of changes from protocol

Reference	Protocol	Change	Justification
SAP Section 1.1.4	Section 2.4.	
The following exploratory endpoints will be included:
 
• European League Against Rheumatism (EULAR) response criteria.• DAS28 remission.• Clinically important change.• Low disease activity.	Additional endpoints considered important for efficacy interpretation by study team.
SAP Section 1.3	Section 8.2.	
Comparison to traditional hypothesis testing has been removed and replaced with a statement that the study is “not sufficiently powered to support hypothesis testing”.
 
The sample size of “n=18” per arm has been updated to “n=10” per arm.
	
Power of the study expected to be lower than that stated in the protocol, given the sample size and expected effect size. Wording updated to remove power calculation.
 
Update to n reflects agreement to close recruitment early. Hence a reduced n per arm was agreed.

SAP Section 4.2.1	Section 8.5.1	Concluded that the difference in mean CFB in DAS28 of AZD9567 - mean CFB in DAS28 of Prednisolone will show a better efficacy if the observed difference negative (less than 0) instead of positive (larger than 0).	Lower DAS28 score is better.

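### SAP 3.5.2 describes the EULAR level of improvement as a mean change in DAS28, where a response counted per subject needs that subject's own change

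*SAP*

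**What the plan says.** Two consecutive sentences in SAP 3.5.2 define how EULAR response is derived.

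- The first defines the quantity: "Improvement (can be either positive or negative and is defined as post-baseline minus baseline) in DAS28 score". It goes on to state that this value is worked out at every planned visit after baseline and then sorted into the cells of SAP Table 1. It does not mention a mean.
- The second gives the rule: "Good, moderate or no response will be determined by the DAS28 score at Day 8, 15 and 28". The score is then set, in the words of the same sentence, "against the level of improvement (mean change from baseline in DAS28 at Day 8, 15 and 28"). Level of improvement is the column heading of Table 1, so this parenthesis describes the column variable, and it calls it a mean.

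Table 1 crosses three columns of improvement (above 1.2, from 0.6 to 1.2, below 0.6) with three rows of attained DAS28 (below 3.2, from 3.2 to 5.1, above 5.1).

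On reporting, SAP 4.3.3.5 says that EULAR response and the other DAS28 categories "will be summarised separately by treatment group and visit to Day 28 using counts and percentages", without formal testing. SAP 4.1.4 adds, as its default rule, that "percentages will be calculated relative to total number of subjects in the analysis set and treatment group".

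Protocol 5.1.1 carries the same table, with rows headed "Background DAS28(CRP/ESR) Score at Time of DAS28 Improvement Assessment" and the same cut-offs. It does not mention a mean.

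**The concern.** A responder percentage is a count of subjects, so every subject must be placed in a cell of Table 1 on that subject's own data. A mean change is one number for a group. If it were used as the column variable, everyone sharing that mean would sit in the same column and only the attained score would separate them. The split between good, moderate and no response would then jump when the mean crossed 0.6 or 1.2, and subjects who had not improved could be counted as responders.

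The wording is not harmless shorthand in this SAP. Section 3.1 uses mean change from baseline in DAS28 for the two arm-level quantities in the primary comparison, so a programmer could take the parenthesis as a pointer to those. SAP section 6 says that the EULAR and related endpoints were added because the study team considered them important for interpreting efficacy. SAP 1.3 says that the trial is not sufficiently powered for hypothesis testing. The descriptive response rates are therefore likely to be read closely.

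**Working it through.** **1. The texts side by side.**

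| Place | What it implies for the unit of classification |
|---|---|
| SAP 3.5.2, first sentence | A value calculated at each scheduled assessment and then categorised: individual, though the words 'each subject' are absent |
| SAP 3.5.2, second sentence, parenthesis | A mean; it does not say whose (arm, pooled or other) |
| SAP 3.5.2, clinically important change | Improvement above 1.2, no mean |
| SAP 4.1.4 and 4.3.3.5 | Counts, with percentages of subjects |
| Protocol 5.1.1 table | Same cut-offs, no mean |

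Only the parenthesis points to a group quantity.

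**2. There is no figure to reproduce.** The documents give no expected EULAR response rate, no expected change in DAS28 and no SD of change. The calculations below show only what the literal reading would do, on assumed inputs.

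**3. Illustration near the 1.2 cut-off.** Assumed: baseline DAS28 normal with mean 4.8 and SD 0.9; individual fall normal with SD 0.9 and independent of baseline; fall counted as positive; the mean taken as the arm mean. The attained score is baseline minus fall, with SD √(0.9² + 0.9²) = 1.273.

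- Arm mean 1.15: by the mean, everyone is in the middle column, so good = 0%. No response = P(score > 5.1) = 1 − Φ((5.1 − 3.65)/1.273) = 13%.
- Arm mean 1.25: by the mean, everyone is in the top column, so no response = 0%. Good = P(score < 3.2) = Φ((3.2 − 3.55)/1.273) = 39%.

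The own-fall column is simulated under Table 1:

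| Arm mean fall | Own fall: good / moderate / none | Arm mean: good / moderate / none |
|---|---|---|
| 1.15 | 29 / 42 / 29% | 0 / 87 / 13% |
| 1.25 | 32 / 42 / 26% | 39 / 61 / 0% |

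Raising baselines below 3.2 to 3.2, to reflect eligibility, changes these by no more than about 0.2 percentage points.

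**4. A wider range.** Assumed: baseline mean 5.0, SD 0.9, values below 3.2 set to 3.2; SD of the fall 0.8 to 1.2; 400,000 simulated subjects per scenario.

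| Mean fall | Own fall: good / moderate / none | Arm mean: good / moderate / none |
|---|---|---|
| 0.5 | 8–15 / 29–33 / 56–59% | 0 / 0 / 100% |
| 0.9 | 17–23 / 34–44 / 39–43% | 0 / 75–80 / 20–25% |
| 1.3 | 29–33 / 37–49 / 23–31% | 34–37 / 63–66 / 0% |

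**5. The sign.** Steps 3 and 4 count a fall as positive. The SAP does not: it takes improvement as post-baseline minus baseline, although section 6 notes "Lower DAS28 score is better". With the written sign, arm means of −1.15 and −1.25 both lie below 0.6, so every subject is a non-responder by the mean. Using each subject's own change but keeping the written sign gives about 99% non-responders at those two means, and 90% to 99.7% over the scenarios in step 4, with no good responders in any of them. Deleting the word *mean* alone would not give a working rule.

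**The case against.** The strongest reply is that the SAP already describes classification per subject. The operative sentence comes first and contains no mean, the outputs are counts of subjects, and the protocol's table has no mean either. The literal rule is also an implausible intention, since any mean fall below 0.6 would make every subject a non-responder. A programmer building a table of subject counts would meet the conflict at once.

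Most of this stands. A reader might infer that the plan classifies subjects by the group average and that the reported response rates will reflect it. The documents do not support that: one parenthesis conflicts with everything around it, and it does not even say whose mean is meant. A reader might also take the move from 0% to 39% good responders as the effect of the rule as written. It is not. It needs an arm mean, a positive sign that the SAP does not use, inputs that the documents do not supply, and two means placed on either side of the 1.2 cut-off.

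What survives is narrower. The first sentence does not say that the value is each subject's own, so the only explicit statement of level in the paragraph is the wrong one. A SAP should leave one reading of a derivation before unblinding.

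**Conclusion.** The parenthesis is wrong as written and conflicts with the rest of the SAP. It should be corrected, as a wording error in a derivation rule. Classification per subject is probably intended, and nothing shows that the group mean will be programmed.

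If it were programmed, the distortion could be large: in the illustrations, good responders differ by up to 29 percentage points (0% against 29% at a mean fall of 1.15) and non-responders by up to 44 (100% against 56% at a mean fall of 0.5). Those sizes rest on assumed baseline and change distributions, on reading the mean as the arm mean, and on counting a fall as positive. They are not estimates for this trial.

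The reach is limited. EULAR response is exploratory and descriptive, and the primary mixed model and the ACR analyses do not use it. The sign conflict in the same paragraph is a separate error. It also touches the clinically important change category and has to be settled in the same edit.

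**What to change.** Make two edits in SAP 3.5.2.

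1. Replace the parenthesis with: *(each subject's own baseline DAS28 minus that subject's DAS28 at that visit, so that a positive value is an improvement)*.
2. In the preceding sentence, change the definition of improvement from post-baseline minus baseline to the same quantity. The clinically important change category then follows the same sign.

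The cost is two phrases in the SAP and the matching lines in the program specification, made before unblinding. No data, design or primary analysis changes.

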4. ANALYSIS METHODS

Statistical analysis will be performed by IQVIA™ using SAS® Version 9.4 or higher.

The derivation of the PK parameters will be performed at Clinical Pharmacokinetic Alliance (Covance). The PK parameters will be derived using non-compartmental methods with Phoenix® WinNonlin® (Version 8.1 or higher), in accordance with “Best Practice Reference Guidelines Pharmacokinetic Evaluations in Clinical Studies”.

4.1 General principles

4.1.1 Reference start date

Study day will be calculated from the reference start date and will be used to show start/stop day of assessments and events.

Reference start date is defined as the date of the first dose of study treatment.

Relative date will be calculated according to the aforementioned reference date as follows:

- If the date of the event is on or after the reference date, then:
 - Study Day = (date of event – reference date) + 1.
- If the date of the event is prior to the reference date, then:
 - Study Day = (date of event – reference date).

Refer to Appendix D Partial and missing date conventions for partial dates for calculating relative day.

4.1.2 Baseline measurements

Baseline is defined as the last non-missing assessment (scheduled or unscheduled) on or prior to reference start date.

In the case where the last non-missing assessment and the reference start date and time coincide, that assessment is considered as occurring before the start of the study treatment dose and the assessment is considered as baseline. However, AEs and medications commencing on the start date and time of first dose will be considered as post-baseline and flagged as treatment-emergent AEs and concomitant medications.

For by visit tables, the screening visit will be presented along with baseline as applicable.

In the case where the assessment time is missing, but reference start date and assessment date coincide, that assessment is considered as occurring before the start of the study treatment dose and the assessment is considered as baseline.

In the case where two assessments exist on the same date on or prior to the reference start date, the assessment with more complete data should be used as baseline, i.e. if time is missing on the one assessment, the assessment with time included should be used as baseline.

There will be no baseline record where the first non-missing assessment is after the reference start date.

4.1.3 Visit windowing

No visit windowing will be implemented. Scheduled visits will be used for analysis purposes.

4.1.4 Table outputs

In general, all summaries will be split by treatment and occasionally added total as follows:

Number (%) of subjects		
AZD9567	Prednisolone	Total

Continuous data will be summarised by descriptive statistics including number of subjects (n), mean, standard deviation (SD), median and range (i.e. minimum value and maximum value). Additionally, the first and third quartiles will be presented for continuous data summaries of exposure data, laboratory parameters and vital signs parameters. For log transformed data, the following descriptive statistics will be presented: number of subjects (n), geometric mean, geometric SD, median and range (i.e. minimum value and maximum value). The mean and median will be presented with one more decimal place than the original data. Standard deviation with two more decimal places than the original data. Minimum and maximum values with the same number of decimal places than the original data.

For categorical data, the variable counts and percentage n (%) per treatment group will be presented. Summaries of continuous variables will be based on non-missing observations. Unless otherwise stated, percentages will be calculated relative to total number of subjects in the analysis set and treatment group. Percentages will be rounded to 1 decimal place.

4.1.5 Statistical modelling

Standard diagnostic approaches will be used to verify that the key statistical assumptions of the mixed model repeated measures (MMRM), ANCOVA and logistic regression models hold.

If the distributional assumptions of the MMRM for the primary analysis do not hold, alternative models will be explored.

4.2 Analysis methods for efficacy variables

4.2.1 Primary efficacy variable analysis method

The difference in change from baseline in DAS28 between AZD9567 and prednisolone (AZD9567 – prednisolone) will be calculated using a mixed model.

4.2.2 Secondary efficacy variable analysis methods

Percentage of subjects achieving ACR20, ACR50 and ACR70 will be analysed with a logistic regression model using PROC GENMOD.

The change from baseline (CFB) in core set measures of ACR and DAS28 will be analysed with a MMRM, using PROC MIXED.

4.3 Statistical models

Prior to unblinding, the difference between countries in DAS28 scores at Day 1 will be tested using a two-sample t-test and if the result is non-significant (p -value $> 5\%$), the country term may be dropped from the primary and secondary models.

4.3.1 Primary efficacy statistical model

Formal statistical testing will be performed for exploratory purposes only.

The default significant level will be two-sided 5%, CIs will be 95% and all tests will be two-sided, unless otherwise specified in the description of the analyses. Two-sided p -value ≤ 0.05 will be considered statistically significant.

Confidence intervals (CIs) for the true difference in means, $\mu_{\text{AZD9567}} - \mu_{\text{Prednisolone}}$, will be calculated using the estimated treatment effect and the mean square error.

A MMRM is to be used to examine the primary efficacy variable, using the PROC MIXED procedure in SAS.

The MMRM model will include the baseline DAS28 score as a covariate.

The MMRM model will include categorical fixed effects of treatment, visit, treatment-by-visit interaction and country:

- Change from baseline (at Day 15) = Treatment group baseline DAS28 score Treatment group*visit
- Treatment group = AZD9567 or Prednisolone.
- Visit = Day 8 and Day 15.
- Country = Netherlands or Sweden
- Change from baseline (at Day 15) = Change in DAS28 from baseline at Day 15.

An unstructured matrix for the within-subject error variance covariance will be used. The denominator degrees of freedom will be calculated according to the Kenward-Roger method.

In case of non-convergence of the preferred model or memory space issues the following models will be explored in the order given:

1. Country may be removed from the model.
2. The second backup model is the same as the preferred model but the Kenward-Roger method will be replaced by Satterthwaite approximation.

The least squares mean (LSM) change from baseline in DAS28 score and corresponding standard error (SE) and 95% confidence interval (CI) by treatment group at Day 8 and Day 15 will be provided in a table. The least squares mean difference (LSMD) between the two

treatment groups at Day 8 and Day 15 and corresponding 95% CI and two-sided p-value will also be presented in the table.

A figure will be provided displaying the LSM change from baseline by treatment group and visit, along with the 95% CI.

The FAS and PP analysis sets will be used for primary efficacy with FAS analysis set as primary interest.

Results for the PP analysis will be tabulated and displayed graphically in the same manner as the primary analysis.

A summary of all continuous efficacy parameters by visit will be provided: DAS28 score, SJC 66, TJC 68, SJC 28, TJC 28, subject's assessment of pain, GH, physician's assessment of global disease activity, subject's assessment of physical function and CRP. DAS28 score will also be summarised separately by visit for the FAS using summary statistics.

4.3.2 Secondary efficacy statistical models

The same MMRM approach for primary variables will be repeated on the following secondary variables:

- Change from baseline in SJC 66.
- Change from baseline in TJC 68.
- Change from baseline in individual components of DAS28 and ACR response:
 - Change from baseline in TJC28.
 - Change from baseline in SJC28.
 - Change from baseline in subject's assessments of global disease activity (GH).
 - Change from baseline in physician's global assessment of disease activity.
 - Change from baseline in subject's assessments of pain.
 - Change from baseline in subject's assessments of physical function.
 - Change from baseline in CRP

The MMRM model for each variable will include the baseline value for the variable of interest as a covariate. Categorical fixed effects of treatment, visit, treatment-by-visit interaction and country will also be included in the model.

A table summarising the results, similar to the primary analysis, will be provided for each endpoint. Figures will not be produced for the above secondary endpoints.

Comparisons between treatment groups regarding the ACR20, ACR50 and ACR70 at Day 8, and 15 will be performed using a logistic regression model for both the FAS and PP analysis sets. The PROC GENMOD procedure in SAS will be used. The covariates of interest are treatment, country and baseline DAS28.

Should there not be sufficient number of observations per outcome category (< 5 in either treatment group) the aforementioned logistic regression will be replaced by a Fisher's exact test.

The number and percentage of subjects achieving ACRxx in each treatment group at Day 8 and Day 15, and the odds ratio and corresponding 95% CI and p-value for the comparison between treatment groups will be summarised in tables for the FAS and PP analysis sets. The proportion of subjects achieving ACRxx at Day 15 will be presented in a bar chart for the FAS and PP analysis sets separately.

No formal statistical hypothesis testing will be carried out on any variables, which will be summarised using standard summary statistics. The aforementioned statistical models are only applied for exploratory purposes.

The FAS will be used for both the secondary and exploratory efficacy endpoints unless otherwise specified.

